## **Study Summary**

v v		
Title	Long term monitoring of patients with cardiac amyloidosis with implantable event monitors	
Running Title	Long term implantable monitors for cardiac amyloidosis.	
IRB Protocol Number	17-006298	
Phase	Pilot	
Overall Study Duration	3 years	
Subject Participation Duration	Approximately six months +31 days if removal	
DurationThere are four specific aims. We seek to determine in wild ty transthyretin amyloidosis (ATTRwt): Specific Aim 1: Burden of conduction system disease and arrhythr specifically sinus node dysfunction, high grade heart block, and A VA, which will identify those who might benefit from a PPM or I Specific Aim 2: Mechanism of SCD (asystole, pulseless electr activity, or sustained VA) and whether this is different in early vs stage amyloidosis. Specific Aim 3: Risk factors for SCA and more specifically wh bradycardia or VA predict SCD, or whether there are imagin 		
Number of Subjects	50	
Diagnosis and Main Inclusion Criteria	Patients with ATTRwt cardiac amyloidosis are included in this study.	
Device	Biomonitor 3 (Utilized not investigational)	
Duration of Exposure	Intended to remain in the body for 6 months pending clinical indications	
Reference therapy	No change in standard of care treatment.	
Statistical Methodology	Pilot Study	

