## 3 Study Design

#### 3.1 General Design

This is a pilot study of 50 patients to monitor arrhythmogensis for six months with +31 days post implantation in patients TTR-wt cardiac amyloidosis proven by endomyocardial biopsy or technetium pyrophosphate scintigraphy. Study staff will provide continuous monitoring of the ILR.

The general design is outlined below:

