#### 4.1 Inclusion Criteria

- 1. Cardiac biopsy or technetium pyrophosphate scintigraphy confirmed patients
- 2. Stage I, II, and early and late stage III in numbers as described, irrespective of EF or NYHA functional class
- 3. Patients aged 18 -85, both genders and of all races and ethnicities.
- 4. Patients must be competent to give informed consent.
- 5. Patients must be able to have the Biomonitor 3 implanted.
- 6. Amyloid stages I-III patients with existing implantable cardiac devices such as pacemakers or defibrillators

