#### 4.3 Subject Recruitment, Enrollment and Screening

Subjects will be screened and recruited from the from the Amyloidosis Clinics, heart failure clinics and respective hospital services. Patients will receive standard of care therapy including staging with cardiac biomarkers. We will recruit 25 patients with stage I or II and 25 patients with stage III. Prior to time of recruitment, inclusion and exclusion criteria will be reviewed for each patient.

There are no known contraindications for the insertion of the BioMonitor 3. However, the patient's particular medical condition may dictate whether or not a subcutaneous, chronically inserted device can be tolerated.

Patients will have the option to leave the device in situ for the lifetime of the device. If opting for the full battery lifetime, the patient/insurance company would be responsible for the continued monitoring after the 6 month study period and the explanation of the device at battery end of life.

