#### 4.4.2 Data Collection and Follow-up for Withdrawn Subjects

Even though a subject has withdrawn from the study, follow-up and survival data on such subjects throughout the protocol defined follow-up period will still need to be collected if possible. Such data is important to the integrity of the final study analysis since early withdrawal could be related to the safety profile of the study device. If a subject withdraws consent to participate in the study, for subject safety reasons, attempts will be made to obtain permission to collect follow up information whenever possible.

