#### Home Monitoring for arrythmias

Telemetry tracings from the implantable monitor will be reviewed monthly or whenever an event occurs and/or a patient transmits data due to symptoms via remote assistance.

Default transmission is data sent daily between 1:00AM and 2:00AM regardless of events. If there is a problem with transmission the device will alert the physician within 24 hours and this will help to maintain compliance of transmission.

If no events occur the device will be interrogated prior to explantation at the end of the 6 month monitoring period.

The study investigators will be responsible for telemetry review. The patient's treating cardiologist will be notified of events of clinical significance. Treatment of the arrhythmias will be based on current clinical guideline recommendations for bradycardia and VA. Clinical follow up will occur via standard of care clinical visits.

SCD is defined as sudden and unexpected death within 1 hour of cardiac symptoms in the absence of progressive cardiac deterioration, unexpected death during sleep, or unexpected death within 24 hours after last being seen alive. Study participants who experience SCD while monitored and are successfully resuscitated after life-threatening VA will receive an implantable cardioverter defibrillator based on current clinical guidelines. These and other arrhythmic events recorded by the implantable monitor, or SCD that cannot be successfully resuscitated, will be considered events of interest and NOT adverse events, as these are not a consequence of monitoring via the implantable device.

At the end of the 6 month monitoring period, the device will be explanted. Participants will be offered the choice to retain the device until battery end of life if clinically indicated. However, patients who opt to continue monitoring will be informed that their insurance

company will be billed for clinically indicated monitoring and explantation outside the study time frame.

For any patients who expire during the study monitoring period, the terminal rhythm of participants who die will be reviewed remotely via the Biotronik website irrespective of whether the monitor can be retrieved. Patients will be informed of this possibility during the consent process.

For stage III patients with existing ICD or pacemakers, rhythm monitoring will be obtained from the device over a 6 month timeframe and may be retrospective if applicable.

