Patients with existing implantable cardiac devices will undergo a device interrogation at enrollment and at the end of the 6 month monitoring period. If available, records from interim routine and unscheduled clinical device interrogations during the 6 month monitoring period be requested for review by the investigators.

Routine clinical follow up will be continued including clinically indicated ECHOs, ECGs,

I imeline for testing:		
Tests		
	At baseline (clinical echo within 6 months of enrollment date) and scheduled as clinically	
ECHO- TTE	indicated	
Biopsy or technetium pyrophosphate scintigraphy	As clinically indicated, inclusion criteria for the study	
pyrophosphate schutgraphy		
	Clinically indicated at baseline (within 6 months of	
EKG	enrollment) and when clinically indicated	
MRI with T1	When clinically indicated	
Cardiopulmonary exercise		
test	When clinically indicated	
Biomonitor 3	Monitored with a clinically significant event	
NT proBNP	When clinically indicated, inclusion criteria for the study based on clinically indicated testing	
	When clinically indicated, inclusion criteria for the	
Troponin T	study based on clinically indicated testing	
Labs: CBC, Basic Metabolic		
Panel, Mg	When clinically indicated	
Urine pregnancy	At baseline for women of child bearing potential	

Timeline for testing:

and blood work.

An insertable monitor may be removed emergently at the investigator's discretion at any time subsequent to an implant procedure. Reasons for removal include, but are not limited to: patient death; loss of sensing; inability to program/interrogate the inserted monitor; infection, EOS (normal or premature); or other reason(s). Complications related to other portions of the insertable monitor system may also result in insertable monitor removal.

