#### Handling of Missing Data

This is a prospective pilot study and all patients will be treated and monitored at Mayo Clinic in Rochester, MN. All clinically relevant data will stored in the Mayo Clinic electronic medical record (Epic). Data queries will be performed at the conclusion of the study to recover any missing data.

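### Stage III device carriers may supply a retrospective rhythm window that other sections do not provide for, and already-paced patients have no stated at-risk denominator for the pacemaker and bradycardia outcomes

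*Combined protocol and SAP*

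**What the plan says.** **Window.** Section 5 (Home Monitoring for arrythmias) states, for stage III patients with an existing ICD or pacemaker, that "rhythm monitoring will be obtained from the device over a 6 month timeframe and may be retrospective if applicable". It does not define when the retrospective option applies. The same section then says, with no limit by stage: "Patients with existing implantable cardiac devices will undergo a device interrogation at enrollment and at the end of the 6 month monitoring period". It adds that interim interrogation records will be requested if available. Section 6.2 (Handling of Missing Data) says: "This is a prospective pilot study and all patients will be treated and monitored at Mayo Clinic in Rochester, MN". Section 3.1 describes the design as one to "monitor arrhythmogensis for six months with +31 days post implantation".

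**Who carries a device.** Section 4.1 item 6 admits patients of stages I to III who already have a pacemaker or defibrillator. Section 4 plans 25 patients with stage I or II and 25 with stage III.

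**Outcomes and analysis.** Primary endpoint 2 (section 3.2) is syncope from heart block or sinus node disease that leads to a pacemaker. Section 3.3 item 2 covers pacemaker implantation, how often pacing is needed, and biventricular pacing. Section 5 lists bradycardia below 35 bpm and heart block among the rhythms of interest. Section 6.2 (Primary Hypothesis) compares arrhythmia burden between stage I–II and stage III with a t-test, and its wording appears to take in carriers of whatever implanted cardiac device. Section 6.3 defines one population: enrolled subjects in whom a device was implanted.

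**The concern.** The retrospective option is attached to stage, the factor being compared. If some stage III patients contribute the six months before enrollment while everyone else contributes the six months after it, the groups differ in how they were observed as well as in disease stage. A pre-enrollment window is also one that the patient must have survived, since section 4.1 requires that "Patients must be competent to give informed consent".

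The second issue is separate and holds however the window is read. A patient who is already paced can hardly reach an endpoint that consists of needing a pacemaker, and pacing hides the slow rates and block that the study sets out to count. If such patients stay in the denominator, the pacemaker and bradycardia rates are too low. If device prevalence differs by stage, the stage contrast is distorted too.

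At stake are pilot estimates that section 6.1 offers as the starting point for larger trials. No powered test is affected.

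**Working it through.** **The plan's own figure.** 25 + 25 = 50 agrees with the stated sample size. Section 6.1 gives no alpha, power, effect size or event rate, so the number itself cannot be re-derived.

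**Part 1: the passages side by side.**

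1. *Who may be retrospective.* Section 5 names stage III carriers. Section 4.1 item 6 admits carriers of stages I to III. No passage gives stage I–II carriers the option. That it is confined to stage III is an inference from silence, since the sentence contains no express limit.
2. *Which window.* Interrogation at enrollment and again six months later describes a window running forward from enrollment. A window that ended at or before enrollment does not fit that schedule. Section 6.2 calls the study prospective without an exception. No passage says which statement governs.
3. *Start date.* Section 3.1 counts from implantation, which works for Biomonitor 3 recipients but not for a device implanted before enrollment. The enrollment interrogation in section 5 suggests a start date for carriers without stating it.
4. *Pooling.* Section 6.2 does not say how the two kinds of window are combined in the t-test.
5. *Direction.* A window that the patient must have survived, and that lies earlier in the disease, could understate stage III burden. Section 4 also recruits from hospital services, so a window leading up to an admission could overstate it. The documents do not settle the sign.
6. *Stage date (minor).* Section 4.3 says "Patients will receive standard of care therapy including staging with cardiac biomarkers", and the section 5 test timetable sets no date for the biomarkers. Stage at enrollment need not be the stage during an earlier window.

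**Part 2: dilution of the pacing outcomes.**

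Inputs: group size 25 (section 4); *m* already-paced patients in a group; true six-month rate *r* among unpaced patients. The documents give neither *m* nor *r*, so both are assumed. Already-paced patients are taken to contribute no events.

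Observed rate = *r* × (25 − *m*) / 25.

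With *r* = 20% in both groups, so no true stage difference (stage I–II versus stage III):

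- 5 versus 5 paced: 0.20 × 20/25 = 16% in each group.
- 5 versus 10 paced: 16% versus 0.20 × 15/25 = 12%.
- 10 versus 5 paced: 12% versus 16%.

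For 5 versus 10 paced, the false difference depends on *r*:

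- *r* = 10%: 8% versus 6%, or 2 points.
- *r* = 20%: 4 points.
- *r* = 30%: 24% versus 18%, or 6 points.

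Equal device counts lower both rates but leave their ratio unchanged. Unequal counts create a contrast whose sign follows the counts.

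**The case against.** The strongest reply on the window is that section 5 is permissive and speaks only of rhythm monitoring. The enrollment interrogation may simply be how stored earlier data are retrieved, and the word prospective is a passing description in a missing-data paragraph. Much of this stands: it makes the problem one of precedence and definition rather than flat contradiction. What remains is an undefined condition, no rule of precedence and no pooling rule, tied to one side of the comparison.

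A reader might go further and infer that deaths, fatal sudden cardiac death and terminal rhythms are lost in stage III. That would follow only if the retrospective window replaced forward follow-up. The sentence does not say so, and the six-month interrogation argues against it. The Study Summary gives participation as "Approximately six months +31 days if removal", and even for withdrawn patients section 4.4.2 says "follow-up and survival data on such subjects throughout the protocol defined follow-up period will still need to be collected if possible". A mortality bias is therefore not shown.

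A reader might also take section 6.2 (Descriptive Statistics) as planning follow-up outcome rates by stage. Its sentence concerns baseline values of the demographic, clinical and outcome variables, so it does not expressly plan such rates. The explicit group test is the one on arrhythmia burden, and Aim 2 compares the mechanism of sudden death by stage.

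On the second part, paced patients remain informative for pacing frequency, shocks, atrial and ventricular arrhythmias and death, and the dilution figures are assumed. Both are fair points. Neither supplies the missing denominator. The section 6.2 wording, read with section 4.1 item 6, suggests that section 6.3 covers existing devices, but section 6.3 does not say so.

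**Conclusion.** Both parts hold in limited form.

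1. As written, the comparison of arrhythmia burden by stage can mix pre-enrollment and post-enrollment windows in the stage III group only. Size and direction are unknown, because the documents do not say how many carriers will be enrolled or how many windows will be retrospective. No loss of deaths is established, and I attach no mortality figure.
2. No at-risk denominator is stated for primary endpoint 2, new pacemaker, or bradycardia and heart block. Leaving already-paced patients in lowers those rates by the fraction paced. Any comparison of them by stage is distorted if that fraction differs. With 5 versus 10 paced of 25, the false difference is 2 to 6 points for assumed true rates of 10% to 30%, and it reverses if the counts are swapped.

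Severity is minor to should-fix: the pilot is unpowered, but its estimates are meant to feed later trials.

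**What to change.** - Reconcile the two statements in section 5 with each other and with section 6.2. For the stage comparison and for all sudden-death and mortality endpoints, use a six-month window for every patient, starting at enrollment for existing-device carriers and at implant for Biomonitor 3 recipients. Record stage at that date.
- Report any retrospective device logs separately and descriptively.
- State in section 6.3 that the population includes carriers of an existing pacemaker or ICD, in line with section 6.2.
- For primary endpoint 2, new pacemaker, and bradycardia or heart block, use as denominator the patients without a pacemaker or active pacing at baseline. State how ICD carriers with backup pacing are classed. Excluding everyone with pacing capability would be a wider rule and could remove ICD carriers who are not being paced.
- Keep already-paced patients in the atrial and ventricular arrhythmia, pacing-frequency and death summaries, and report device counts by stage.

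The cost is protocol and SAP wording plus one baseline device flag known at screening. Section 5 already schedules the interrogations, and the sample size stays at 50. The downside is fewer patients in the bradycardia and pacemaker summaries.

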## 6 Statistical Plan

Page 29 of 40

#### 6.1 Sample Size Determination

This study is a pilot study, to assess the true arrhythmic burden seen in the TTR-wt population. This is a novel study design and no research exists. This study will provide the basis for future, larger scale trials.

#### 6.2 Statistical Methods

#### **Descriptive Statistics**

Univariate descriptive statistics and frequency distributions will be calculated, as appropriate for all variables. Baseline values for demographic, clinical, and outcome variables (primary and secondary) will be tabulated for the two groups. These analyses will help identify baseline clinical characteristics that may be associated with risk of sudden cardiac arrest or bradycardia requiring pacemaker implantation.

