Currently, the balance of data does not support ICD implantation in amyloid cardiomyopathy (7). However, some studies have demonstrated that ventricular arrhythmias resulting in SCD can be successfully treated with defibrillation, hypothesizing that this treatment may be more successful in earlier stage disease (8,26,27). SCD in late stage disease has been hypothesized to be due to electromechanical dissociation or bradycardia mediated asystole for which an ICD would not be beneficial (25)(8,18). The Mayo clinic staging system based on cardiac biomarkers has been validated and is used to stratify severity of disease (early vs late stage) in TTR-wt cardiomyopathy. The reported 4 year survival estimates of patients with Mayo stage I (TnT <0.05ng/ml and NT BNP <3000 pg/mL), II (either TnT >0.05 ng/ml or NT BNP >3000 pg/mL), and III (TnT >0.05 ng/ml and NT BNP >3000 pg/mL) TTRwt amyloidosis was 57%, 42%, and 18%, respectively (28). Those patients with advanced amyloid cardiomyopathy may have estimated survival less than a year due to heart failure and should be excluded from ICD whereas those with earlier stage may still have added survival benefit. We hypothesize that the occurrence and treatibility of ventricular arrhythmias is dependent on disease progression and may be a phenomena of earlier stage disease. Monitoring at all stages of CA disease to understand arrhythmia risk at each stage is instrumental in understanding the true prevalence and treatment of arrhythmias.

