## 2 Study Objectives

Listed below are the specific aims/objectives for this study.

**Specific Aim 1**: Burden of conduction system disease and arrhythmias, specifically sinus node dysfunction, high grade heart block, and AF and VA, which will identify those who might benefit from a PPM or ICD

**Specific Aim 2**: Mechanism of SCD (asystole, pulseless electrical activity, or sustained VA) and whether this is different in early vs. late stage amyloidosis.

**Specific Aim 3**: Risk factors for SCA and more specifically whether bradycardia or VA predict SCD, or whether there are imaging or clinical characteristics that predict SCA **Specific Aim 4**: Utility of long term ECG monitoring in TTR-wt cardiomyopathy

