#### **Primary Hypothesis:**

The primary hypothesis that arrhythmogenesis and SCD risk in this population is influenced by amyloid cardiomyopathy stage rather than reduced left ventricular ejection fraction, which is often a marker of late disease and increased mortality due to heart failure, and that SCD due to asystole, rather than VA which could be treated with ICD. Conduction system disease causing heart block, atrial arrhythmias and VA leading to SCD may occur earlier in the disease process and treatment of AF, VA, and heart block could improve both morbidity and mortality.

A Student's t-test will be used to compare differences in arrhythmia burden between the patients in the two groups (early stage I-II vs stage III either with any implanted cardiac device).

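### Section 6.2 tabulates by stage group and never by outcome, so for any characteristic other than stage it cannot show an association with cardiac arrest or pacemaker need

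*Combined protocol and SAP*

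**What the plan says.** Aim 3 (section 2) is to find "Risk factors for SCA and more specifically whether bradycardia or VA predict SCD, or whether there are imaging or clinical characteristics that predict SCA". Section 3.3 adds two secondary endpoints on how well NSVT and atrial flutter or fibrillation predict sudden cardiac death.

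The Descriptive Statistics part of section 6.2 offers one-variable summaries and frequency distributions, followed by this table: "Baseline values for demographic, clinical, and outcome variables (primary and secondary) will be tabulated for the two groups". It then assigns the purpose: "These analyses will help identify baseline clinical characteristics that may be associated with risk of sudden cardiac arrest or bradycardia requiring pacemaker implantation".

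That paragraph does not define the groups. The Primary Hypothesis part of the same section does, in describing "the two groups (early stage I-II vs stage III either with any implanted cardiac device". Sections 4 and 4.3 set matching quotas of 25 stage I or II patients and 25 stage III patients. No other grouping appears in the protocol.

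The only other method given is this: "A Student's t-test will be used to compare differences in arrhythmia burden between the patients in the two groups". Section 6.3 defines an analysis population and adds no analysis.

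**The concern.** A table with stage as its column variable answers one question: what differs between early and late stage? Aim 3 asks another: what differs between patients who do and do not have an event? The plan offers the first table as a help towards the second question.

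Three things are at stake.

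- **Aim 3.** Apart from stage, no imaging or clinical characteristic is set against arrest or pacemaker need. Nor are monitored bradycardia, VA, NSVT or AF.
- **The primary hypothesis.** It holds that stage, and not a reduced ejection fraction, drives arrhythmia and SCD risk. Ejection fraction tabulated by stage is never compared with SCD, so that half of the contrast is untested.
- **Interpretation.** Some variables separate the stage groups by construction. Section 1.4.1 defines stage "III (TnT >0.05 ng/ml and NT BNP >3000 pg/mL", so both biomarkers will differ between the columns whatever their relation to arrest. A real risk characteristic that is balanced across stage would show nothing.

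Section 6.1 presents the pilot as the basis for larger trials, so the choice of candidate risk factors to carry forward matters.

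**Working it through.** The plan states no alpha, power, effect size or event count, so there is no figure of its own to reproduce. The check has three steps.

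**1. Which analyses relate what to what**

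| Statement in section 6 | Relates | Characteristic vs event? |
|---|---|---|
| One-variable summaries | nothing to anything | no |
| Table for the two groups | each variable to stage | only for stage itself |
| Student's t-test | arrhythmia burden to stage | no |
| Section 6.3 | population definition | no |

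The second row reads the table as including outcomes seen during follow-up, from the words "outcome variables (primary and secondary) will be tabulated for the two groups".

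**2. Can the stage table determine the association?**

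Take an illustrative characteristic X and fix everything the planned table would show:

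- stage I-II: 10/25 have X, 2/25 have an event;
- stage III: 15/25 have X, 5/25 have an event.

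Overall, 25 patients have X, 25 do not, and there are 7 events. The following splits all fit these margins:

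| Events with X, stage I-II + stage III | With X | Without X | Fisher p |
|---|---|---|---|
| 2 + 5 | 7/25 | 0/25 | 0.0096 |
| 1 + 3 | 4/25 | 3/25 | 1.0 |
| 0 + 0 | 0/25 | 7/25 | 0.0096, opposite direction |

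The planned table is identical in all three. The p-values only mark how far apart the cases are; the plan puts no test on this table.

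**3. What a table by outcome could deliver**

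*Expected deaths.* Section 1.4.1 gives four-year survival of 57%, 42% and 18% for stages I, II and III. Assuming a constant hazard, the six-month risk is 1 − S^(0.5/4):

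- stage I: 1 − 0.57^0.125 = 6.8%
- stage II: 1 − 0.42^0.125 = 10.3%
- stage III: 1 − 0.18^0.125 = 19.3%

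The stage I-II group of 25 then has between 25 × 0.068 = 1.7 deaths (all stage I) and 25 × 0.103 = 2.6 (all stage II). Stage III has 25 × 0.193 = 4.8. The total is 6.5 to 7.4 deaths from any cause.

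*Expected sudden deaths.* The documents give no sudden-death share. If 25% to 75% of deaths are sudden (assumed), the range is 0.25 × 6.5 = 1.6 to 0.75 × 7.4 = 5.5, or about 3% to 11% of 50 patients. Resuscitated arrests would add to this; no rate is given for them. No pacemaker rate for this population is given either.

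*Precision.* For a characteristic that splits the cohort 25/25, with every event on one side, two-sided Fisher gives p = 0.0502 with 5 events and p = 0.022 with 6. At least 6 one-sided events are needed to reach 0.05.

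Now assume a characteristic present in 40% (20 vs 30 patients) with a fourfold risk. At overall event rate r, the risk without the characteristic is r/(0.4 × 4 + 0.6) = r/2.2. Exact Fisher power is:

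| Arrest rate r | Risk without / with | Power |
|---|---|---|
| 3% | 1.4% / 5.5% | 1.5% |
| 5% | 2.3% / 9.1% | 6% |
| 10% | 4.5% / 18.2% | 27% |

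**The case against.** Four objections deserve weight.

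- **The table does relate one characteristic to outcome.** Stage is a baseline characteristic and outcomes are tabulated by stage. A reader might infer that the plan never sets any characteristic against an event. That goes too far: stage, and through it troponin T and NT-proBNP in coarse form, is set against outcome, and stage is central to the primary hypothesis. This objection stands, and the point is limited to other characteristics.
- **The plan's sentence is hedged and descriptive.** It speaks of helping to identify characteristics that may be associated, and attaches no test. A reader might infer that stage correlates will be published as arrest risk factors. The documents do not say so. Still, hedging does not supply the missing comparison: step 2 shows the table is compatible with either direction of association.
- **The grouping is inferred.** The Descriptive Statistics paragraph leaves the two groups undefined. The stage reading is nevertheless the only one the protocol supports.
- **It is a pilot with few events.** A reader might infer that a table by outcome would detect risk factors reliably. At event rates of 20% or 30% power would look good, but the protocol's survival figures do not support such rates for arrest. This limits what the repair can achieve and lowers the severity. It excuses low power, but not tabulating against the wrong variable. Because the data will exist anyway, the omission can be put right before analysis.

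**Conclusion.** The point holds for every characteristic except stage. Section 6.2 credits a table by stage with helping to identify risk characteristics, which that table cannot do, and no other analysis in section 6 fills the gap. Aim 3, the ejection-fraction half of the primary hypothesis, and the NSVT and AF prediction endpoints are left without a method.

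That conclusion rests on reading the two groups as stage groups and needs no numerical assumption. The size of what can be recovered does need assumptions: a constant hazard applied to all-cause four-year survival, and a 25% to 75% sudden share. On those, about 2 to 6 sudden deaths are expected among 50 patients, with power of 1.5% to 27% for a fourfold risk at arrest rates of 3% to 10%. The pacemaker outcome cannot be sized from the documents.

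This should be fixed. It does not undermine the study as a whole: it affects mainly one of four aims, in a pilot whose answer on that aim would be imprecise even after repair.

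**What to change.** 1. Keep the stage table as a description of the groups, state that the groups are stage I-II and stage III, and limit the sentence about identifying characteristics to stage.
2. Add one table, labelled exploratory, comparing patients with and without each outcome: (a) SCD or resuscitated arrest; (b) bradycardia requiring a pacemaker. State how patients who enter with a pacemaker or defibrillator (inclusion criterion 6) are counted in (b).
3. Prespecify the rows:
   - entry characteristics, including ejection fraction, stage, ECG, troponin T and NT-proBNP;
   - monitored bradycardia, VA, NSVT and AF, counting only what was recorded before the event and giving the monitored time. Entry measures alone would miss Aim 3's own question about bradycardia and VA.
   - For MRI and exercise testing, which section 5 schedules only when clinically indicated, give the number measured.
4. Report counts and unadjusted estimates with exact 95% confidence intervals, and show the counts by stage group. Fit stratified or penalised models only if event numbers allow; on a handful of arrests they would be close to uninformative.

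The cost is a few sentences and one table from data already collected. The drawback is wide intervals, which should be shown as such, with the results described as hypothesis-generating.
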